### ***Missing date and time of first IMP administration***

When the date and time of the first IMP administration is missing, all **adverse events** that occurred on or after the day of randomization should be considered as treatment-emergent adverse events.

The **exposure duration** should be kept as missing.

### ***Missing assessment of relationship of AEs to IMP***

If the assessment of the relationship to IMP is missing, then the relationship to IMP has to be assumed and the adverse event considered as such in the frequency tables of possibly related adverse events, but no imputation should be done at the data level.

### ***Missing severity of adverse events***

If the severity is missing for 1 of the treatment-emergent occurrences of an adverse event, the maximal severity on the remaining occurrences will be considered. If the severity is missing for all the occurrences, a “missing” category will be added in the summary table.

### ***Missing data while evaluating PCSAs***

Participants missing baseline will be grouped in the category “normal/missing at baseline.”

For PCSAs with 2 conditions, one based on a change from baseline value or a normal range and the other on a threshold value, with the first condition being missing, the PCSA will be based only on the second condition.

For a PCSA defined on a threshold and/or a normal range, this PCSA will be derived using this threshold if the normal range is missing; eg, for eosinophils the PCSA is  $> 0.5$  GIGA/L or  $>ULN$  if  $ULN \geq 0.5$  GIGA/L. When ULN is missing, the value 0.5 should be used.

Measurements flagged as invalid by the laboratory will not be summarized or taken into account in the computation of PCSA values.

## 5.4.5 Timepoint assessment

### Analysis windows for time points

For VAS for rhinosinusitis, Vital signs, and Laboratory assessments. The analysis windows post baseline of [Table 10](#) will be generated.

A measurement (scheduled or unscheduled) will be used if it is available and measurement date is within the analysis window.

After applying these time windows, if multiple assessments are associated to the same time point, the closest from the targeted study day will be used. If the difference is a tie, the value after the targeted study day will be used. If multiple valid values exist within a same day, then the first value of the day will be selected.

If there is no measurement for a given parameter in an analysis window, data will be considered missing for the corresponding visit.

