1.2 SCHEMA

Figure 1 - Graphical study design

Abbreviations: D: day; EOS: end of study, EOT: end of treatment; q2w: every 2 weeks; q4w: every 4 weeks; V: visit.

Procedure	D-28 to D-14	Intervention Period							
		W0 D1	W2 D15 (±3 days)	W4 D29 (±3 days)	W8 D57 (±3 days)	W16 D113 (±3 days)	W24 D169 (±3 days)	W40 D281 (±3 days)	W52 D364 (±3 days) EOT/EOS
Visit	V1 (Screening)	V2	V3	V4	V5	V6	V7	V8	V9
CT scan	X ^e						X		X
Nasal Symptom Diary ^f (includes nasal congestion, loss of smell, anterior and posterior rhinorrhea; TSS derived from these 4 items)		←————— daily diary —————→							
VAS for rhinosinusitis		X	X	X	X	X	X	X	X
Vital signs ^g	X	X			X	X	X	X	X
12-Lead ECG (local reading)	X								
AE review		←—————							
SAE review		←—————							
Laboratory assessments (including hematology, biochemistry, and urinalysis) ^h	X	X			X		X		X
Hepatitis B and C; HIV testing; TB testing ⁱ	X					X ^j	X ^j	X ^j	X ^j
Pregnancy test (WOCBP only) ^k	X	X		X	X	X (W12, 16)	X (W20, 24)	X (W28, 32, 36, 40)	X (W44, 48, 52)

Abbreviations: AE: adverse event; CT: computerized tomography; D: day; e-CRF: electronic case report form; ECG: electrocardiogram; EOS: end of study; EOT: end of treatment; HBcAb: hepatitis B core antibody; HBsAb: hepatitis B surface antibody; HBsAg: hepatitis B surface antigen; HCV Ab: hepatitis C virus antibody; HIV: human immunodeficiency virus; IgM: immunoglobulin M; IGAR: Interferon-gamma release assay; IMP: investigational medicinal product; IVRS/IWRS: interactive voice/web response system; MRI: magnetic resonance image; NE: nasal endoscopy; NERD: non-steroid anti-inflammatory drug exacerbated respiratory disease; NP: nasal polyposis; NPS: nasal polyp score; q2w: every 2 weeks; q4w: every 4 weeks; SAE: serious adverse event; SCS: systemic corticosteroids; TB: tuberculosis; TSS: total symptom score; V: visit; VAS: visual analogue scale; W: week; WOCBP: women of childbearing potential.

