Participants who receive any of the prohibited treatments or undergo surgery during the Screening Period will not start the intervention period. They may, however, be rescreened following the procedures described in the SoA ([Section 1.3](#)).

Participants who use INCS between Visit 2 and Week 24 for whatever reason will discontinue the IMP administration.

Permitted concomitant medication

The following treatments are allowed throughout the study unless otherwise specified:

- Intranasal corticosteroids to treat other coexisting diseases (such as allergic rhinitis) are allowed after Week 24 as needed.
- Nasal normal saline.
- Single topical decongestant administration such as oxymetazoline hydrochloride (to reduce swelling and widen the path for the endoscope) and topical anesthetics such as lidocaine are allowed before endoscopy.
- Short-acting $\beta 2$ -adrenergic receptor agonists, long-acting $\beta 2$ -adrenergic receptor agonists, and long-acting muscarinic acetylcholine receptor antagonists.
- Methylxanthines (eg, theophylline, aminophyllines).
- Inhaled corticosteroids.
- Systemic antihistamines.

- Leukotriene antagonists/modifiers are permitted during the study, only for participants who were on a continuous treatment for ≥ 30 days before Visit 1.
- Allergen immunotherapy in place for ≥ 3 months before Visit 1 is permitted.
- Paracetamol/Acetaminophen, at doses of ≤ 2 g/day, is permitted for use any time during the study.

Other concomitant medication may be considered on a case-by-case basis by the Investigator in consultation with the Medical Monitor if required.

Rescue medication including antibiotics, short courses of SCS for treatment of CRSwNP as described in [Section 6.8.1](#), or short courses of SCS to treat other serious coexisting diseases (such as asthma exacerbation) or for AEs is allowed.

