9.3.2 Primary efficacy endpoint

- The proportion of responders (NPS improvement from baseline ≥ 1) at Week 24.

The number of participants and percentage with the 95% confidence interval (CI) for the primary endpoint will be provided at Week 24 in the PP population.

Participants who undergo surgery for NP or receive SCS for any reason will be considered nonresponders for time points after undergoing surgery or receiving SCS. Participants who have missing data at Week 24 will be considered nonresponders.

Details of supportive analyses will be provided in the SAP.

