# 1 INTRODUCTION

## 1.1 STUDY DESIGN

This is a 52-week, Phase 4, open-label, single-arm, multicenter study to assess the efficacy and safety of dupilumab as monotherapy without concomitant intranasal corticosteroid (INCS) in approximately 25 participants 18 years and older with chronic rhinosinusitis with nasal polyposis (CRSwNP) not adequately controlled with existing therapies.

After a screening phase of 2 to 4 weeks, participants will be treated with dupilumab 300 mg q2w without concomitant administration of INCS for approximately 24 weeks. For participants who have stable disease, the dosing interval can be changed from q2w to q4w at the discretion of the Investigator at Week 24. Participants who change from q2w to q4w will not be permitted to return to the q2w regimen during this study and will receive the q4w regimen until Week 48. Other participants will receive the q2w regimen up to Week 50. The participants will be followed up to Week 52.

Figure 1 - Graphical study design

Study analysis will be conducted after study completion.

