**Table 10 - Analysis window definition**

Scheduled visit post baseline	Target day	Nasal endoscopy	CT scan	VAS for rhinosinusitis	Vital signs	Laboratory assessments
V3 (W2)	15	-	-	1+ to 21	-	-
V4 (W4)	29	1+ to 42	-	22 to 42	-	-
V5 (W8)	57	43 to 84	-	43 to 84	1+ to 84	1+ to 112
V6 (W16)	113	85 to 140	-	85 to 140	85 to 140	-
V7 (W24)	169	141 to 224	1+ to 265	141 to 224	141 to 224	113 to 265
V8 (W40)	281	225 to 321	-	225 to 321	225 to 321	-
V9 (W52)	364	322 =<	266 =<	322 =<	322 =<	266 =<

1+: after 1st dose date/time

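### SAP Table 10's Week 24 windows can admit an early CT, or an endoscopy or CT taken after INCS has started, in place of the planned missing-data rules

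*SAP*

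**What the plan says.** The protocol's schedule of activities places the Week 24 visit (V7) at Day 169, ±3 days. SAP Table 10 assigns to V7 an endoscopy on Days 141 to 224 and a CT from 1+ to Day 265, where 1+ means "after 1 st dose date/time". The Week 52 CT window opens on Day 266.

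The rule for using a value is "A measurement (scheduled or unscheduled) will be used if it is available and measurement date is within the analysis window". Where several values qualify, "if multiple assessments are associated to the same time point, the closest from the targeted study day will be used". Week 24 is missing only if the window is empty. The sentence that introduces Table 10 reads "For VAS for rhinosinusitis, Vital signs, and Laboratory assessments" and mentions neither endoscopy nor CT, although the table has a column for each.

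Treatment conditions can change at Week 24. On dosing, for participants with stable disease, "the dosing interval can be changed from q2w to q4w at the discretion of the Investigator at Week 24" (SAP 1.1). On INCS, "Intranasal corticosteroids to treat other coexisting diseases (such as allergic rhinitis) are allowed after Week 24 as needed" (Protocol 6.8).

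The planned rules for absent data are these. For the primary endpoint, "Participants who have missing data at Week 24 will be considered nonresponders" (Protocol 9.3.2, repeated in SAP 4.3.2). For the change-from-baseline endpoints, SAP 4.4.1.2 uses a hybrid of worst observation carried forward (WOCF) and multiple imputation.

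**The concern.** The primary objective concerns 24 weeks of q2w dosing without INCS. A window that extends past the point where INCS and q4w become possible can label as Week 24 a value that was not obtained under those conditions. A window that opens at the first dose can label as Week 24 a CT that reflects only a few weeks of exposure.

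In both cases the value counts as observed, so the rule written for a missing Week 24 value never operates. For the primary endpoint this works in one direction: a participant who would otherwise be a nonresponder either stays one or becomes a responder. For LMK, a key secondary endpoint, an early value in effect carries forward one observation where multiple imputation was intended.

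**Working it through.** **1. The plan's own figure.** Inputs from Protocol 9.1: responder rate 62.0%, 20 evaluable participants, target of at least 50%, 20% drop-out. The exact binomial gives P(X ≥ 10 | n = 20, p = 0.62) = 0.908 against the stated 90%, and 20/(1 − 0.20) = 25. Both are reproduced. They do not depend on the windows, but they give the denominators and the criterion used in step 5.

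**2. Window widths around Day 169.**

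| Window | Days | Length | Reach before target | Reach after target |
|---|---|---|---|---|
| Protocol visit | 166–172 | 7 | 3 | 3 |
| Endoscopy, V7 | 141–224 | 84 | 169 − 141 = 28 | 224 − 169 = 55 |
| CT, V7 | 1+–265 | 265 | 169 − 1 = 168 | 265 − 169 = 96 |

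The Week 52 CT window opens 364 − 266 = 98 days before its target. The limits essentially follow midpoints between scheduled assessments: (113 + 169)/2 = 141, (169 + 281)/2 = 225, (169 + 364)/2 = 266.5. They are not tied to exposure or regimen.

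**3. Does another rule remove a value taken after Week 24?**
- INCS: the per-protocol (PP) population excludes INCS use only up to Week 24. The SAP 4.1 definition of rescue covers surgery and systemic corticosteroids, not INCS. The mITT supplementary analysis handles INCS only up to Week 24. Nothing removes a Day 210 endoscopy or CT from a participant who started INCS for allergic rhinitis on, say, Day 190.
- q4w: if the Week 24 dose is given on Day 169, the first omitted q2w dose falls on Day 169 + 14 = 183. That leaves 265 − 183 + 1 = 83 days of the CT window in which the value could be taken on q4w. The endoscopy window has 224 − 183 + 1 = 42 such days. However, the switch itself requires an NPS improvement of at least 2 at both Weeks 16 and 24. An NPS taken on q4w can therefore fill Week 24 only if the central Week 24 reading is missing and the switch rested on some other reading. The documents do not say which reading governs the switch.

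**4. Early CT.** CT is scheduled only in screening and at Weeks 24 and 52, so a CT well before Day 169 is off-schedule. If one exists, say on Day 29 (169 − 29 = 140 days early), and no later CT falls in the window, Table 10 makes it the Week 24 LMK. For a participant who stopped for a reason other than lack of efficacy, the planned multiple imputation is then not applied. For a lack-of-efficacy stop, SAP 4.4.1.2 is less clear. Its opening text keeps data collected after the stop and uses WOCF only if Week 24 is still missing, while its listed steps set those data to missing.

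**5. Size for the primary endpoint.** One participant is worth 1/25 = 4 points or 1/20 = 5 points. At n = 25, one participant separates 12/25 = 48% from 13/25 = 52%.

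As an illustration, assume 25 in PP, a true rate of 62%, and k participants whose only endoscopy in the window is off-schedule. The documents give no k. If those k count as nonresponders, the expected rate is 0.62 × (25 − k)/25 and success needs at least 13 responders among 25 − k.

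| k | Expected rate | P(at least 13/25) |
|---|---|---|
| 0 | 62.0% | 0.891 |
| 1 | 59.5% | 0.842 |
| 2 | 57.0% | 0.777 |
| 4 | 52.1% | 0.599 |

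If the off-schedule values are used and respond at 62%, the figures stay at 62.0% and 0.891 for every k.

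**The case against.** The strongest reply is the closest-to-target rule. A usable reading on Day 169 ±3 displaces any other, and no endoscopy or CT is scheduled between V7 and V8 (Day 281 ±3). The wide window therefore acts only when the Week 24 assessment was missed or unreadable and an off-schedule one exists. This stands and limits the frequency. It does not supply a rule for those participants, and off-schedule endoscopies are foreseen: Protocol 6.8.1 asks for one before systemic corticosteroids.

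Second, Protocol 2.3.2 reports that the INCS-only placebo groups of the earlier Phase 3 studies showed no improving trend in NPS or LMK. The distortion from INCS may therefore be small. That is fair as to size, but the study exists to describe treatment without INCS.

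Third, midpoint windows are conventional, and Protocol Appendix 7 lets endoscopy and CT visits run late in an emergency. This is a good reason not to cut the endoscopy window simply for being wide.

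Fourth, the lead-in and the unscheduled-visits paragraph of SAP 5.4.5 do not mention endoscopy or CT, so the windows might not govern them. In that case the SAP gives no window for either, and the text needs correcting on both readings.

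A reader might infer that everyone who stops early contributes an early CT as Week 24. The documents do not support that. The opening of Protocol 7.1.1 excepts CT from the assessments after permanent discontinuation, while the closing paragraph of 7.1.1, and sections 6.8.1 and 7.2, refer to the end-of-treatment assessments without that exception.

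**Conclusion.** The point holds in a limited form. For participants with no usable value near Day 169, Table 10 can (a) count an off-schedule CT from weeks or months earlier as the observed Week 24 LMK, and (b) count in PP an endoscopy or CT taken after INCS became permitted, replacing nonresponse for the primary endpoint. The q4w route is open for CT and narrow for NPS.

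The size is 4 to 5 percentage points on the primary proportion per affected participant, and only where the off-schedule value shows a response. The number affected cannot be derived from the documents, and the table in step 5 rests on an assumed k. No hypothesis is tested, but the conclusion of similarity rests on a point estimate against 50%, which one participant can decide.

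A reader might go further and conclude that the Week 24 results will be substantially made up of q4w or INCS values. The documents do not support this, given the closest-to-target rule and the stable-disease condition for the switch. The diary endpoints are not in Table 10 and are unaffected. The Week 52 CT window raises the same issue of timing, but for an exploratory, descriptive endpoint.

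**What to change.** In SAP section 5.4.5 and Table 10:

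- Replace the V7 CT lower bound of 1+ with one near the visit, for example Day 141 as for endoscopy. Start the V9 CT window nearer Week 52, for example Day 322 as for endoscopy.
- State that a Week 24 efficacy value must precede any INCS started after Week 24 and the first departure from q2w dosing. Treat any other value as missing under the nonresponder, WOCF and multiple-imputation rules already planned.
- Keep late values within the existing endoscopy window, including emergency-extended visits, if they meet that condition.
- Name endoscopy and CT in the lead-in, and say whether unscheduled ones are windowed.

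Separately, the CT exception in the opening of Protocol 7.1.1 must be reconciled with the closing paragraph of 7.1.1 and with sections 6.8.1 and 7.2.

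The cost is mostly SAP wording, with no new data collection. With the example bounds, CTs before Day 141 or on Days 266 to 321 would belong to no visit; none is scheduled then. A few values would become missing, which may lower the responder rate slightly or increase the amount of imputation.

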**Table 10 - Analysis window definition**

Scheduled visit post baseline	Target day	Nasal endoscopy	CT scan	VAS for rhinosinusitis	Vital signs	Laboratory assessments
V3 (W2)	15	-	-	1+ to 21	-	-
V4 (W4)	29	1+ to 42	-	22 to 42	-	-
V5 (W8)	57	43 to 84	-	43 to 84	1+ to 84	1+ to 112
V6 (W16)	113	85 to 140	-	85 to 140	85 to 140	-
V7 (W24)	169	141 to 224	1+ to 265	141 to 224	141 to 224	113 to 265
V8 (W40)	281	225 to 321	-	225 to 321	225 to 321	-
V9 (W52)	364	322 =<	266 =<	322 =<	322 =<	266 =<

1+: after 1st dose date/time

### Unscheduled visits

Unscheduled visit measurements of laboratory data and vital signs will be used for computation of baseline, the last on-treatment value, analysis according to PCSAs, and the shift summaries for safety. They will also be included in the by-visit summaries if they are re-allocated to scheduled visits.

## 5.5 APPENDIX 5 POTENTIALLY CLINICALLY SIGNIFICANT ABNORMALITIES CRITERIA

**Table 11 - Criteria for Potentially Significant Abnormalities – for Phase 2/3 studies**

Parameter	PCSA	Comments
Clinical Chemistry		
ALT	By distribution analysis: >3 ULN >5 ULN >10 ULN >20 ULN	Enzymes activities must be expressed in ULN, not in IU/L. Concept paper on DILI – FDA draft Guidance Oct 2007. Internal DILI WG Oct 2008. Categories are cumulative. First row is mandatory. Rows following one mentioning zero can be deleted.
AST	By distribution analysis: >3 ULN >5 ULN >10 ULN >20 ULN	Enzymes activities must be expressed in ULN, not in IU/L. Concept paper on DILI – FDA draft Guidance Oct 2007. Internal DILI WG Oct 2008. Categories are cumulative. First row is mandatory. Rows following one mentioning zero can be deleted.
Alkaline Phosphatase	>1.5 ULN	Enzymes activities must be expressed in ULN, not in IU/L. Concept paper on DILI – FDA draft Guidance Oct 2007. Internal DILI WG Oct 2008.
Total Bilirubin	>1.5 ULN >2 ULN	Must be expressed in ULN, not in $\mu\text{mol/L}$ or $\text{mg/L}$ . Categories are cumulative. Concept paper on DILI – FDA draft Guidance Oct 2007. Internal DILI WG Oct 2008.
Conjugated Bilirubin	>35% Total Bilirubin and TBILI >1.5 ULN	Conjugated bilirubin dosed on a case-by-case basis.
ALT and Total Bilirubin	ALT >3 ULN and TBILI >2 ULN	Concept paper on DILI – FDA draft Guidance Oct 2007. Internal DILI WG Oct 2008. To be counted within a same treatment phase, whatever the interval between measurement.
CPK	>3 ULN >10 ULN	FDA Feb 2005. Am J Cardiol April 2006. Categories are cumulative. First row is mandatory. Rows following one mentioning zero can be deleted.

Parameter	PCSA	Comments
CLcr (mL/min) (Estimated creatinine clearance based on the Cokcroft-Gault equation)	<15 (end stage renal disease) ≥15 - <30 (severe decrease in GFR) ≥30 - < 60 (moderate decrease in GFR) ≥60 - <90 (mild decrease in GFR) ≥ 90 (normal GFR)	FDA draft Guidance 2010 Pharmacokinetics in patients with impaired renal function-study design, data analysis, and impact on dosing and labeling
eGFR (mL/min/1.73m2) (Estimate of GFR based on an MDRD equation)	<15 (end stage renal disease) ≥15 - <30 (severe decrease in GFR) ≥30 - < 60 (moderate decrease in GFR) ≥60 - <90 (mild decrease in GFR) ≥ 90 (normal GFR)	FDA draft Guidance 2010 Pharmacokinetics in patients with impaired renal function-study design, data analysis, and impact on dosing and labeling
Creatinine	≥150 µmol/L (Adults) ≥30% change from baseline ≥100% change from baseline	Benichou C., 1994.
Uric Acid Hyperuricemia Hypouricemia	>408 µmol/L <120 µmol/L	Harrison- Principles of internal Medicine 17 th Ed., 2008.
Blood Urea Nitrogen	≥17 mmol/L	
Chloride	<80 mmol/L >115 mmol/L	
Sodium	≤129 mmol/L ≥160 mmol/L	
Potassium	<3 mmol/L ≥5.5 mmol/L	FDA Feb 2005.
Total Cholesterol	≥7.74 mmol/L	Threshold for therapeutic intervention.
Triglycerides	≥4.6 mmol/L	Threshold for therapeutic intervention.
Lipasemia	≥3 ULN	
Amylasemia	≥3 ULN	
Glucose Hypoglycaemia Hyperglycaemia	≤3.9 mmol/L and <LLN ≥11.1 mmol/L (unfasted); ≥7 mmol/L (fasted)	ADA May 2005. ADA Jan 2008.
HbA1c	>8%	
Albumin	≤25 g/L	
CRP	>2 ULN or >10 mg/L (if ULN not provided)	FDA Sept 2005.
Hematology		

Parameter	PCSA	Comments
WBC	<3.0 Giga/L (Non-Black); <2.0 Giga/L (Black) ≥16.0 Giga/L	Increase in WBC: not relevant. To be interpreted only if no differential count available.
Lymphocytes	>4.0 Giga/L	
Neutrophils	<1.5 Giga/L (Non-Black); <1.0 Giga/L (Black)	International Consensus meeting on drug-induced blood cytopenias, 1991. FDA criteria.
Monocytes	>0.7 Giga/L	
Basophils	>0.1 Giga/L	
Eosinophils	>0.5 Giga/L or >ULN (if ULN ≥0.5 Giga/L)	Harrison- Principles of internal Medicine 17 th Ed., 2008.
Hemoglobin	≤115 g/L (Male); ≤95 g/L (Female) ≥185 g/L (Male); ≥165 g/L (Female)  Decrease from Baseline ≥20 g/L	Criteria based upon decrease from baseline are more relevant than based on absolute value. Other categories for decrease from baseline can be used (≥30 g/L, ≥40 g/L, ≥50 g/L).
Hematocrit	≤0.37 v/v (Male) ; ≤0.32 v/v (Female) ≥0.55 v/v (Male) ; ≥0.5 v/v (Female)	
RBC	≥6 Tera/L	Unless specifically required for particular drug development, the analysis is redundant with that of Hb. Otherwise, consider FDA criteria.
Platelets	<100 Giga/L ≥700 Giga/L	International Consensus meeting on drug-induced blood cytopenias, 1991.
Urinalysis		
pH	≤4.6 ≥8	
Vital signs		
HR	≤50 bpm and decrease from baseline ≥20 bpm ≥120 bpm and increase from baseline ≥20 bpm	To be applied for all positions (including missing) except STANDING.
SBP	≤95 mmHg and decrease from baseline ≥20mmHg ≥160 mmHg and increase from baseline ≥20 mmHg	To be applied for all positions (including missing) except STANDING.
DBP	≤45 mmHg and decrease from baseline ≥10 mmHg ≥110 mmHg and increase from baseline ≥10 mmHg	To be applied for all positions (including missing) except STANDING.

Parameter	PCSA	Comments
Orthostatic Hypotension		
Orthostatic SDB	≤-20 mmHg	
Orthostatic DBP	≤-10 mmHg	
Weight	≥5% increase from baseline ≥5% decrease from baseline	FDA Feb 2007.

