Participants with known helminth infections were excluded from participation in clinical studies; therefore, it is not known if dupilumab will influence the immune response against helminth infections. Consequently, participants with pre-existing helminth infections should be treated for their helminth infection before initiating therapy with dupilumab.

Other potential risks based on the safety profile in particular indications such as eosinophilia in asthma participants treated with dupilumab monotherapy were reported in 2 asthma studies. However, eosinophil counts declined to near baseline levels during study treatment. It is anticipated that dupilumab used as monotherapy in Japanese participants with CRSwNP will have a favorable safety profile, as observed in the Phase 3 global clinical program for this disease (with concomitant INCS administration) and across other type 2-driven immunological disorders.

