9.3.5.2 Laboratory variables and vital signs

Quantitative analyses

For laboratory variables, vital signs, descriptive statistics for results, and changes from baseline will be provided for each planned visit, with the last value and the worst value (minimum and/or maximum value depending on the parameter) during the treatment-emergent period. These analyses will be performed using central measurements (when available) or local measurements for laboratory variables.

Analyses according to PCSA

Potentially clinically significant abnormality analyses will be performed based on the PCSA list currently in effect at Sanofi at the time of database lock. Analyses according to PCSA will be performed based on the worst value during the treatment-emergent period, using all measurements (either local or central, and scheduled, nonscheduled, or repeated). For laboratory variables and vital signs, the incidence of participants with at least one PCSA during the treatment-emergent period will be summarized, regardless of the baseline level, according to the following baseline status categories:

- Normal/missing
- Abnormal according to PCSA criterion or criteria

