### 4.7.3 Additional safety assessments

#### 4.7.3.1 Laboratory variables, vital signs and electrocardiograms (ECGs)

The following laboratory variables and vital signs will be converted into standard international units and analyzed.

- Hematology:
  - Red blood cells and platelets and coagulation: [hemoglobin, hematocrit, red blood cell count, platelet count
  - White blood cells: white blood cell count, neutrophils, lymphocytes, monocytes, basophils, eosinophils
- Clinical chemistry:
  - Metabolism: glucose, total cholesterol, total protein, albumin, creatine phosphokinase
  - Electrolytes: sodium, potassium, chloride
  - Renal function: creatinine, blood urea nitrogen, uric acid.  
Creatinine clearance will be derived with the equation of Cockcroft and Gault using weight assessed at the same visit as creatinine. eGFR will be derived using the Modification of the Diet in Renal Disease (MDRD) equation.
  - Liver function: alanine aminotransferase, aspartate aminotransferase, alkaline phosphatase, lactate dehydrogenase, total bilirubin
  - Pregnancy test: Serum and urine  $\beta$ -human chorionic gonadotropin (all childbearing potential female participants)
- Urinalysis:

- Urinalysis for quantitative analysis: pH, specific gravity, glucose, protein, blood, ketones, urobilinogen, nitrite by dipstick
- Vital signs:
  - pulse rate, systolic and diastolic blood pressure, weight, respiratory rate, temperature

ECG data are used for screening purposes only.

Data below the lower limit of quantitation/detection limit (LLOQ) will be replaced by half of the LLOQ, data above the upper limit of quantification will be replaced by ULOQ value.

Grading (LLN, ULN) will be derived using local laboratory normal ranges.

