### **Quantitative analyses**

For all laboratory variables and vital signs above, descriptive statistics for results and changes from baseline will be provided for each planned visit during the on-treatment period. These analyses will be performed using local measurements, converted into SI units for laboratory variables.

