### **Analyses according to PCSA**

Potentially clinically significant abnormality (PCSA) analyses will be performed based on the PCSA list currently in effect at Sanofi at the time of the database lock. Parameters with no PCSA criteria defined, similar analyses will be done using the local normal ranges, if applicable.

Analyses according to PCSA will be performed based on the worst value during the treatment-emergent period, using all measurements.

For laboratory variables and vital signs above, the incidence of participants with at least one PCSA during the treatment-emergent period will be summarized regardless of the baseline level and according to the following baseline status categories:

- Normal/missing
- Abnormal according to PCSA criterion or criteria

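### The SAP omits the protocol's last-value and worst-value laboratory summaries without logging it, so no planned table grades each participant's peak eosinophil count

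*SAP*

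**What the plan says.** Protocol 2.3.1 lists eosinophilia among the identified adverse drug reactions. As a potential risk it notes that "eosinophilia in asthma participants treated with dupilumab monotherapy were reported in 2 asthma studies", and adds that counts later came back close to baseline while treatment continued.

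Protocol 9.3.5.2 plans descriptive statistics for laboratory values and changes at each planned visit, "with the last value and the worst value (minimum and/or maximum value depending on the parameter) during the treatment-emergent period".

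SAP 4.7.3.1 includes eosinophils among the variables analysed ("White blood cells: white blood cell count, neutrophils, lymphocytes, monocytes, basophils, eosinophils"). Its quantitative paragraph says that "descriptive statistics for results and changes from baseline will be provided for each planned visit during the on-treatment period", and mentions neither the last nor the worst value.

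The PCSA paragraph of SAP 4.7.3.1 does use extremes: "Analyses according to PCSA will be performed based on the worst value during the treatment-emergent period, using all measurements". Results are given overall and by baseline status, normal or missing against "Abnormal according to PCSA criterion or criteria". For eosinophils, SAP Table 11 sets the single criterion ">0.5 Giga/L or >ULN (if ULN ≥0.5 Giga/L". In the same table ALT, AST and CPK have cumulative tiers and creatinine has change-from-baseline criteria. For hemoglobin the table comments that "Criteria based upon decrease from baseline are more relevant than based on absolute value".

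SAP Appendix 2 logs two departures from the protocol, the treatment-emergent period and the rescue definition. The Version History states that there are no major changes.

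**The concern.** The risk the protocol describes is a rise followed by a fall, so the informative quantity is each participant's peak relative to their own starting count. The omitted worst-value summary is the one that would have carried it.

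The remaining laboratory outputs can miss a peak in two ways. The eligibility criteria set no eosinophil limit, so some participants may enter above 0.5 Giga/L, and for them the PCSA flag cannot tell a stable count from a marked rise. Routine on-treatment samples are planned only at Weeks 8, 24 and 52, and where a window holds several samples only one enters the by-visit table.

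Safety of monotherapy is a stated objective. At stake is whether the report can say how many of about 25 participants had a marked rise, and how large the largest rises were.

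**Working it through.** **1. Protocol against SAP.**

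| Output for laboratory variables | Protocol 9.3.5.2 | SAP 4.7.3.1 |
|---|---|---|
| Value and change at each planned visit | Yes | Yes |
| Last treatment-emergent value | Yes | Not specified |
| Worst treatment-emergent value, summarised | Yes | Not specified |
| Worst value, as PCSA yes/no | Yes | Yes |

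The removal is not in Appendix 2. SAP 5.4.5, under unscheduled visits, still refers to a last on-treatment value and to shift summaries that section 4.7.3 never defines. That suggests an unreconciled omission rather than a decision.

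**2. The Table 11 rule on hypothetical counts** (Giga/L, ULN not above 0.5).

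| Baseline | Peak | Change | Baseline status | PCSA |
|---|---|---|---|---|
| 0.3 | 0.45 | +0.15 | normal | no |
| 0.3 | 0.8 | +0.5 | normal | yes |
| 0.6 | 0.6 | 0 | abnormal | yes |
| 0.6 | 1.6 | +1.0 | abnormal | yes |
| 0.6 | 3.2 | +2.6 | abnormal | yes |
| 0.6 | 5.5 | +4.9 | abnormal | yes |

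The last four rows share one cell. The first two show that the rule does discriminate among participants normal at baseline.

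**3. The window rule.** In SAP Table 10 the Week 8 laboratory window runs from after the first dose to Day 112, with target Day 57. SAP 5.4.5 keeps the sample nearest the target. Take 0.7 on Day 57 and an unscheduled 3.2 on Day 80. The distances are |57 − 57| = 0 and |80 − 57| = 23, so the Week 8 table takes 0.7. The 3.2 then enters the planned laboratory tables only as a PCSA yes, and appears elsewhere only if reported as an adverse event.

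**4. Size, by assumption.** The documents give no baseline eosinophil distribution. Assume lognormal counts with median m from 0.25 to 0.60 Giga/L, between-person log SD 0.6, within-person log SD 0.3, three post-baseline samples, and either no drug effect or a doubling.

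Share above 0.5 at baseline = 1 − Φ[ln(0.5/m) / √(0.6² + 0.3²)], where √0.45 = 0.671.

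- m = 0.25: 0.693/0.671 = 1.03, giving 15%, or about 4 of 25.
- m = 0.60: −0.182/0.671 = −0.27, giving 61%, or about 15 of 25.

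Simulation with 400,000 draws per scenario gives:

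| Output | m = 0.25: none → doubling | m = 0.60: none → doubling |
|---|---|---|
| PCSA, abnormal at baseline | 82% → about 100% | 95% → about 100% |
| PCSA, normal at baseline | 14% → 59% | 44% → 90% |
| PCSA, overall | 24% → 65% | 75% → 96% |
| Peak above 1.5 Giga/L (illustrative level) | 1% → 9% | 15% → 52% |

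The abnormal-baseline row hardly moves. The normal-baseline row moves a great deal. A graded row would also move, and it would cover the participants whom the single cut-off cannot separate.

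The result depends on the SDs. With 0.4 and 0.2 in place of 0.6 and 0.3, √0.20 = 0.447, and the share starting above 0.5 at m = 0.25 falls to 6%.

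**The case against.** A reader might infer that eosinophilia is tabulated only against the 0.5 cut-off, that marked rises go unreported, or that the PCSA output is mostly uninformative. The documents do not support any of these.

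- SAP Table 9 has an eosinophilia row built on CMQ10641, reported as number and percentage of participants. Its footnote takes in all cases, symptomatic or not. Protocol 8.3.6 also makes symptomatic eosinophilia an event of special interest with immediate notification.
- Eosinophil values and changes from baseline are summarised at each planned visit. Where the SAP spells out continuous summaries it lists minimum and maximum. If that set applies here, a large rise at Week 8, 24 or 52 would probably be visible among about 25 participants.
- The PCSA analysis still uses the worst value from all measurements, and the normal-baseline row responds strongly in the table above.
- A single cut-off is not itself an error. Several other parameters in Table 11 have one, and the SAP applies the sponsor's list in force at database lock, so Table 11 may be superseded. The safety endpoints are adverse-event incidences, not laboratory grades.

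All of this stands, and it narrows the point without removing it. The adverse-event count depends on investigator reporting: Protocol 8.2.4 and 10.3.1 leave out laboratory abnormalities tied to the underlying disease unless they are more severe than expected. A per-visit maximum shows one extreme, not how many participants had marked rises, and it misses a peak that the window rule passes over.

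**Conclusion.** The concern holds in a limited form. There is an unlogged difference between protocol and SAP: the last-value and worst-value summaries are gone for every laboratory and vital-sign variable. For eosinophils this combines with the single cut-off and the nearest-to-target rule. As a result, no planned table grades each participant's peak or gives the largest change from own baseline, and the PCSA table cannot separate stable from markedly rising counts in participants already above 0.5 Giga/L.

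The text comparison, the cell example and the window example need no assumption about the eosinophil distribution. The number affected does. The range of 15% to 61% starting above 0.5 rests on assumed medians and SDs, and drops to 6% at the low end with smaller SDs. The 1.5 Giga/L level has no source in the documents and is used only to illustrate. The primary efficacy analysis and the adverse-event endpoints are not affected. This is a low-cost improvement to safety reporting, not a defect that undermines the trial.

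**What to change.** In SAP 4.7.3.1, restore the protocol's last-value and worst-value summaries, as value and change from baseline, using all scheduled and unscheduled treatment-emergent samples. If the omission was intended, log and justify it in Appendix 2. Reconcile the section with SAP 5.4.5, either by defining the last on-treatment value and shift summaries there or by deleting the reference.

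For eosinophils, add the maximum change from own baseline, together with either higher reporting categories by baseline status, prespecified by the sponsor, or a by-participant listing. These are reporting categories only and change nothing in clinical management.

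The data are already collected. The cost is SAP wording and one table or listing for about 25 participants; the downside is a few more rows in the safety output.
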